D.3.b. MNA Identification Phase: Subjects will be shown how MedMinder™ works and demonstrate proficiency in loading and activating the device. They will be told their doctors will receive summary reports on their med intake patterns. The tray plugs into a standard 110v outlet, has 28 compartments allowing up to 4 dose times per day for 7 days, and is capable of providing escalating reminder signals (described in D.5.a). **Reminder functions will be disabled for the 1-month screening phase.** The nurse manager (or project manager, [name]) and subject will program the MedMinder for dosing times (example of subject's 24-hr MedMinder activity in Appx. 23). Subject will receive written and oral instructions on MA criteria (i.e., all meds taken within 180 min window centered on prescribed dosing time). SMASH app has auto call feature for TACHL service line for technical issues. Time and date stamped opening and closure of the tray's compartments are relayed via GSM wireless cellular transmitter/receiver to MedMinder™ server for processing. The encrypted data are sent to a HIPPA-compliant server database housed in the TACHL center. The MA formula will be used to calculate MA scores.^{22,23,52,121} (see Appx. 2) **Only subjects with MA score < 0.85 over the 4 week screening and whose subsequent resting and 24-hr SBP evaluations reconfirm uncontrolled HTN will be eligible for enrollment into the RCT.** [name] will randomly assign the 8 sites to either SMASH or

enhanced SC conditions.

D.4. Time Table (Table 2) Based on our SMASH trials, we will recruit 16 subjects/mo beginning mo 4 and finish recruiting by mo 15. We will provide a smart phone and/or service plan for ~40 SMASHers we project might lose phones or service plans during the trial.^{20,21,25,27} Post-trial data collection will finish in mo 34. Post study focus groups and subsequent qualitative analyses will end in mo 43. Table 2 presents a timetable for the study.

Activity	Month
Set-up	Mos 1-3
Recruitment	Mos 4-15
Intervention	Mos 5-22
Follow-up	Mos 16-34
Focus Groups	Mos 35-37
Statistical analyses	Mos 23-28
Prep. and Submission of Effectiveness RCT RO1	Mos 36-42
	Mos 43-48
Month	0 2 4 6 8 10 12 14 16 18 20 22 24 26 28 30 32 34 36 38 40 42 44 46 48
Year	1 2 3 4

D.5. SMASH Protocol:

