D.5.a. Patient Level: Subjects whose practice site is randomly assigned the SMASH condition are termed **SMASHers**. The nurse manager or [name] will confirm with the doctor and patient the med regimen and times meds will be taken daily (example of subject’s 24-hr MedMinder activity in Appx. 23). **SMASHers will have MedMinder’s reminder functions activated.** (Enhanced SC care group will not receive reminders, see D.5.c.) Initially, the designated pill compartment on the tray (28 compartments for up to 4 doses/day for 7 days) emits a bright white blinking light for 30 minutes when it is time to take the meds. If the compartment is not opened, cup removed and emptied within that time, an intermittent chime ensues for 30 minutes. If the cup is not opened, removed, emptied and returned during that time period, the subject receives an automated SMS or voicemail according to his/her preference. They will be provided and instructed on use of the validated Bluetooth-enabled UA-767 Plus BP monitor.¹²² The SMASH app will be installed on their phone that includes audio, text and graphic step-by-step instructions with countdown timers for the 3 readings over the 10 min protocol, and a 1-min refresher training video. BP data are securely received on the phone and sent to the TACHL-housed server. SMASHers will receive written and oral info on adherence criteria: 1) take all meds within 180 min window (90 min before or after dosing times); 2) take BP every 3 days in morning and evening (protocol in Appx. 24). They will correctly load and operate the tray, use the app and BP monitor before leaving the clinic.

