Smashers will complete the values, beliefs and life goals questionnaire (VBG; see Appx. 14). Responses are used in a tree-structured algorithm to select tailored motivational and positive reinforcement SMS or voicemail messages based on previous day’s MA levels. Examples of motivational messaging based upon patients’ responses are provided in C.1.5 and Appx. 4. After 2 consecutive weeks of 100% MA (typically first 2-4 weeks), messages are switched from daily to a variable interval schedule averaging 2 messages/week. Cumulative MA graphs will be sent on their phones weekly during the 6-month trial (MA rate algorithm in Appx. 2). Automated SMS messages will remind subjects to self-measure BP every 3 days. After each BP session, the SMASH app provides audio and visual BP feedback, and opportunity to see BP averages charted over time and against JNC8 guidelines (screenshot example in Appx. 25).

SMASHers will receive 30-45 sec audio or SMS messages 2x/week on HTN facts (e.g., HTN is permanent, uncontrolled HTN is silent killer), importance of timely, consistent MA, tips on expressing questions /concerns with MD (e.g., side effects; examples in Appx. 26). SMASHers will have auto dial feature on their app for [name] (or TACHL service techs if needed) to address technology related issues should they arise.

D.5.b. Provider Level: SMASH primary providers will receive summary reports, designed by them, using patient ID#s every week based upon their preference (e.g., email; NexGen EMR with email reminder to view it; example in Appx. 27). They will receive email reminders for viewing generated reports as needed every 6 hrs for 24hr period. They (and the SC MDs) will receive the same summary charts of JNC8 BP management guidelines used by us in other studies^{22,23,25} (Example in Appx. 28). If a SMASHer’s mean BP exceeds thresholds (e.g., BP >180/ 105 or <100/75 mmHg) during a session, [name] will receive an SMS alert, call the patient and conduct the BP protocol again. If BP still exceeds thresholds, FQHC providers have requested their nurse managers be called to do a follow-up with the patient.

D.5.c. Enhanced Standard Care (SC) Protocol: Subjects whose practice site is randomized to the SC group will continue to use the tray with reminder functions disabled for another 6 months. To **help maximize rigor**

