Cost-effectiveness analyses will be run using established methodology for economic evaluation of electronic drug monitoring for MNA.¹⁵⁴ Data will be collected on incremental direct and time cost SMASH program adds to enhanced SC for facilitating MA and BP control. This includes personnel costs for referral & BP/ MA screening, all supplies and equipment used (MedMinders, BP devices, smart phones/ data packages) and costs of additional meds beyond SC. Value of project manager's time will be included in attending to patient assistance calls, verification of out of range BPs, etc. Sensitivity analyses will estimate cost changes related to different types of personnel time needed to perform her tasks. We will define benefits as difference in cost of health services use and lost worked days between SMASH and SC groups. We will compare costs of emergency department (ED), outpatient and hospital visits during the 6-month trial and most importantly, the 12 months following trial completion. We will use estimates from the Healthcare Cost and Utilization Project¹⁴⁵ for ED and hospitalization and the Medical Expenditure Panel Survey¹⁴⁴ (for outpatient and individual out-of-pocket costs) to value healthcare use costs in each group. Thus, healthcare costs will be evaluated at institutional provider, third party payer and individual level and all costs adjusted using inflation adjustment from Bureau of Labor Statistics.¹⁵⁵ We will estimate cost of lost worked days during the 6-mo trial and 12-mo follow-up and reported baseline income. We will assess differences in means, medians and quartiles based on distribution of the variables. As we did in another telehealth project, we will use GLM with appropriate distribution to examine association of SMASH with patient level healthcare costs and patient lost income adjusting for patient demographics and comorbidities.¹⁵⁶ We will conduct sensitivity analyses by estimating different healthcare costs and income models while adjusting for clinical outcomes (e.g., % with JNC8 BP control; % with 24-hr BP control). We will do the same for healthcare utilization and lost workdays using a count model (Poisson or Neg Bin if over dispersion occurs or zero-inflated if many zeros are present). We will perform a comparison of SMASH cost with changes in clinical outcomes to provide cost-effectiveness ratios for clinical outcomes.

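### The cost-effectiveness plan counts items that both arms receive as incremental to SMASH, and leaves undefined whether the ratio's numerator is gross programme cost or net cost

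*Combined protocol and SAP*

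**What the plan says.** All the plan says on how costs are combined is in the cost-effectiveness paragraph of D.10, AIM 3.

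- **Cost basis:** "Data will be collected on incremental direct and time cost SMASH program adds to enhanced SC for facilitating MA and BP control".
- **Items in it:** "This includes personnel costs for referral & BP/ MA screening, all supplies and equipment used (MedMinders, BP devices, smart phones/ data packages"; also medication costs beyond SC and the project manager's time.
- **Benefits:** "We will define benefits as difference in cost of health services use and lost worked days between SMASH and SC groups". These are compared over the 6-month trial and the 12 months after it, and the later period is called the more important. They are modelled separately.
- **Ratio:** a "comparison of SMASH cost with changes in clinical outcomes to provide cost-effectiveness ratios for clinical outcomes". No formula follows.

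Other sections show who receives what.

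- **D.3.b**, on entry to the trial in either arm: "Only subjects with MA score < 0.85 over the 4 week screening and whose subsequent resting and 24-hr SBP evaluations reconfirm uncontrolled HTN" are eligible.
- **D.5.c**, on SC subjects: they "will continue to use the tray with reminder functions disabled for another 6 months". They also receive automated messages, links to short videos every 3 days, or mailed brochures.
- **D.5.a**, on SMASH subjects: "They will be provided and instructed on use of the validated Bluetooth-enabled UA-767 Plus BP monitor".
- **D.4:** "We will provide a smart phone and/or service plan for ~40 SMASHers".
- **Table 3** has a single cost-effectiveness row that lists personnel time and devices together with emergency-department (ED) visits, unplanned outpatient visits, hospitalizations and lost workdays.

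**The concern.** An incremental cost contains only what one arm uses beyond the other. Screening and trays are used in both arms, so charging them to SMASH contradicts the paragraph's own definition. Leaving out what SC spends on its attention-control material pushes the figure the same way.

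The second problem is the numerator. A cost-effectiveness ratio against a comparator normally divides the difference in total cost by the difference in effect. The plan itemises programme cost, places health-service and workday differences under a different name, and then builds the ratio from SMASH cost alone. An analyst could follow this text to either of two quite different ratios, and could choose after seeing the data.

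At stake is Aim 3b, the trial's economic evidence. Section A.5 links the programme's testing to later adoption and to reimbursement by public and private payers. A ratio built on the wrong increment, or on an unstated one, would not serve that use.

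**Working it through.** **Step 1. Which listed items are incremental to enhanced SC?**

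| Item listed in D.10 | SMASH | SC | Incremental? |
|---|---|---|---|
| BP/MA screening personnel | yes (D.3.a, D.3.b) | yes (same) | no |
| MedMinder tray | yes, reminders on (D.5.a) | yes, reminders off, 6 months (D.5.c) | no |
| Home BP monitor | yes (D.5.a) | no | yes |
| Supplied phones or data plans | about 40 subjects (D.4) | none stated | yes |
| SC messages, videos, brochures | no | yes (D.5.c) | SC cost; no offset listed |

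**Step 2. Reproduce the only money figures.** C.1.4, Trial #2, gives ED visits before and during the trial as 7 and 3 (SMASH) and 13 and 12 (SC), with savings of USD 23,692 and USD 5,923.

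- SMASH: 23,692 / (7 − 3) = 5,923 per visit.
- SC: 5,923 / (13 − 12) = 5,923 per visit.

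Both figures follow from one unit cost. The percentages printed beside them do not match the counts: 4/7 = 57.1% (printed 57.5%) and 1/13 = 7.7% (printed 5.7%). This does not affect the dollar figures.

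**Step 3. Size of the possible offset.**

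- Difference in savings: 23,692 − 5,923 = USD 17,769, which is 3 visits.
- D.8 gives 22 patients for this pilot but no arm sizes. Assuming 11 per arm: 17,769 / 11 = USD 1,615 per SMASH patient.
- With 10 SMASH and 12 SC: 23,692/10 − 5,923/12 = USD 1,876. With 12 and 10: 23,692/12 − 5,923/10 = USD 1,382.

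This is a difference in before-after change. The plan's benefit is a between-arm difference. Taking in-trial visits only, (12 − 3) × 5,923 = USD 53,307, or USD 4,846 per patient at 11 per arm. The pilot therefore cannot fix a magnitude.

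**Step 4. What the offset would do to a ratio.** Let P be programme cost per SMASH patient (not in the documents; assumed), H the offset of Step 3 (1,615, unrounded in the table), and ΔE = 0.30, the planning difference in D.8.

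- Gross ratio = P / ΔE.
- Net ratio = (P − H) / ΔE.

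| Assumed P (USD) | Gross ratio | Net ratio |
|---|---|---|
| 1,000 | 3,333 | −2,051 |
| 2,000 | 6,667 | 1,282 |
| 3,000 | 10,000 | 4,615 |

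The sign differs only when P is below H. A negative entry means lower cost with better outcome and should not be read as a price.

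**Step 5. Shared items alone.** If 25% of an assumed P of 2,000 were trays and screening, removing it gives 2,000 × 0.75 / 0.30 = USD 5,000 per extra controlled patient instead of 6,667. The ratio is lower but still positive. The 25% is an assumption; the documents do not split the cost.

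**The case against.** **The list may only name cost categories to be differenced.** On that reading screening and trays cancel, because the governing phrase is incremental to enhanced SC. This is possible. But the text calls for all supplies and equipment used, names trays, and says nothing about recording or subtracting SC's amounts. The inconsistency stands as wording to be corrected.

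**A clinic adopting SMASH would have to buy trays.** This is a fair point about roll-out. It requires a comparator of usual care without trays, and the plan names enhanced SC. Such a figure is legitimate as a separately labelled scenario.

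**Reporting savings apart from programme cost can be informative.** D.10 values health-care cost at provider, payer and individual level, and ED savings need not return to the clinic that pays. This stands, and it means that any net ratio must state a perspective.

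**A net numerator is not excluded.** A reader might infer that the savings are definitely left out of the ratio. The documents do not establish this: D.10 gives no formula, and Table 3 puts programme and health-service items in one cost-effectiveness row.

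**The ratio need not have the wrong sign.** A reader might also infer from Step 4 that it will. That needs a programme cost below the offset. No programme cost is given, and the offset rests on a net 3 ED visits in 22 patients, with assumed arm sizes and no hospital, outpatient or post-trial costs. If SMASH increased service use, omitting it would flatter SMASH instead.

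**Conclusion.** The concern holds in two parts of different strength.

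- **Shared items: established as a conflict within the document.** Screening and trays are listed as cost that SMASH adds, although SC receives both, and SC's own material has no listed offset. If followed as written, this overstates incremental cost against enhanced SC. By how much is unknown.
- **Numerator: undefined.** Taken literally it is gross programme cost and omits health-service and workday differences. The text does not settle the matter.

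Neither the size nor the sign of the combined effect can be determined from the documents. The figure of about USD 1,615 per SMASH patient (USD 1,382 to 1,876 for the other splits tried) shows that the offset could be material, and no more. This is an exploratory outcome. The primary outcomes, sample size and power are untouched. It should be corrected before the cost data are analysed.

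**What to change.** Amend the cost-effectiveness paragraph of D.10:

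1. Define the main ratio as (SMASH minus SC difference in total cost) / (SMASH minus SC difference in proportion controlled). Total cost is programme plus health services.
2. State the perspective and include or exclude lost workdays accordingly. State the horizon, for example 6 months or 18 months.
3. Count screening and trays in both arms or in neither. Cost SC's messages, videos and brochures.
4. Report lower cost with better outcome as dominance, not as a negative ratio.
5. If wanted, give gross programme cost per outcome, or a roll-out comparison with usual care without trays, as separately labelled scenarios.

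The cost is a change of wording, simple logging of SC programme costs by arm, and slightly more analysis work. No change to design, visits or sample size is needed.

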OVERALL IMPACT, SIGNIFICANCE, INVESTIGATOR(S) & INNOVATION: *inclusion/exclusion criteria not in grant (R1&R2).* We apologize for placing too much of that info in Human Subjects. It is now in section D.2 (and Human Subjects [1.a.]) *Unclear how nonadherence due to smartphone service loss will be handled (R1):* In our feasibility trials we observed high BP monitoring adherence via phone app (~88%), nonadherence tended to occur when cellular service was disrupted. We budgeted for 40% to receive a smart phone or data package to cover phone or service loss during the trial (in D.4.) *Justify relatively limited age range (21-59 yrs) (R1):* We are recruiting AAs from a federally qualified health center (FQHC) with sole diagnosis of HTN (n=2,619; mean age ~45.3 yrs). Majority of those ≥ 60 had multiple comorbidities & JNC8 BP control goals differ for patients <60 vs ≥60. *Concern PI may not have time (25%FTE) to devote to project (R1):* Within 2 mos of start date for this grant, [name] will be covered 50% FTE on grants (R21 & RO1 will have expired; see bio). He has a long track record of running successful concurrent trials. An experienced full time project manager has been added, [name]. *Consider adding someone with usability testing background (R1):* [name] is a consultant with expertise in user centered, iterative design in web/app programs including use of various usability evaluation tactics (e.g., expert heuristic & end user think aloud evals, questionnaires; see bio & letter). *SMASH not highly innovative, been used in other patient groups(R1):* Our patient centered design revealed significant heterogeneity of influence of cultural heritage/acclimation and numeracy of chronic diseases (single vs multi-morbidities) upon MA and other health behaviors within & across ethnic groups. The mHealth program tailored to Hispanics is not culturally attuned for AAs. Our mHealth work with AA renal transplant patients with HTN, diabetes, etc. led to efforts to address poor MA before multi-morbidities develop. Our long-term goal is to prevent common events (e.g., stroke, heart attack) & slow progression of common comorbidities (e.g., chronic kidney disease, diabetes) due to uncontrolled HTN. SMASH for transplant patients required ~2 years of changes to become salient to AAs with solely uncontrolled HTN. We found those with only HTN often have greater MA problems (in C.1.3) & to be more challenging to establish sustained regimen adherence compared to HTNs with multi-morbidities. Experiences during trials & post trial interviews led to an iterative process of identifying highly salient motivational factors (values, beliefs, goals) not needed with multi-morbidity transplant patients (in C.1.5.) Others have observed similar challenges with single vs multi-morbidity HTN patients (in A.2.) This program (nor any earlier iteration) has not been nor is being tested using a fully powered RCT, much less within a low-income population & health system (i.e., FQHC). *No focus on med nonadherence (MNA) mechanisms besides self-motivation or how other diseases & meds affect HTN MA; no lit review on comorbidities(R2):* We clarified HTNs with comorbidities aren't recruited (in D.2.) Exploratory analyses of MNA mechanisms now include med side effects, stress, depression symptoms, etc. (in D.10.) We added diabetes /CVD risk factor changes (e.g., TC, HgA1c) as exploratory outcomes. Recent trials show some newer HTN meds lower or at least do not increase these risk factors (in A.2.) **APPROACH & ENVIRONMENT:** *Limited description of clinics (R1):* 7 of 8 clinics have similar numbers of AAs with uncontrolled HTN and numbers of primary providers (MD, PA, NP; M=2.4). Lead site has 7.3 providers & generates ~45% of patient encounters (in Facilities & Resources). Clinic (=cluster) in our cluster RCT design will be a random effect in the analytic model & account for clinic site differences (in D.10). *More details on SMASH focus group protocol stratification process (R1):* We will identify 2 groups: 16 MA responders & 16 partial/nonresponders stratified by clinic, age & sex. We will run 3-4 focus groups separately by group classification (in D.7.) *Measures of numeracy, usability & project evaluation needed; SMASH & control condition descriptions a bit vague (R1):* We added measures (in D.6.) & reworded SMASH & SC protocols for clarity (in D5-7.) *No model to guide analytic approach; how will data be integrated to provide cohesive story (R1):* We clarified in D.10 our conceptual model is built upon Self-Determination Theory with competence & autonomous motivation as primary MA mediators. We now include socio-demographic (e.g., age, income) & biobehavioral (e.g., med side effects, stress, sleep quality, etc.) factors as potential moderators & mediators of MA. Those results will guide an integrated causal model using structural equation modeling that will identify key active ingredients of SMASH to guide future refinements.

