cutoffs compared to 25-40% for the SC group. They also showed significant increases in MPR (mean of 0.90 across trial) compared to the SC group (mean of 0.50 across trial). We also examined emergency department (ED) utilization rates during the 6-mo periods prior to and during the trial.²⁵ The SMASH group showed a 57.5% reduction (7 vs 3 ED visits) whereas the SC group showed a 5.7% reduction (13 vs 12 ED visits). This equated to a savings of \$23,692 in the SMASH group compared to \$5,923 in the SC group compared to the previous 6 months. We will assess cost effectiveness in the proposed trial as an exploratory outcome. **Our proposed trial will use patients from this FQHC.**

[figure not shown]
SMASH Post Stroke AAs with HTN Trial # 3: After the initial grant submission, we completed a 3-mo trial with 3-mo follow-up with AAs just released from hospital following a first incident stroke. **Their only pre-existing diagnosis was HTN.** We used the SMASH program described in trial #2. These findings were recently published and noted high acceptability (90% recruitment rate; 96% retention rate), usability (e.g., easy to learn and use; both scores ≥ 4.25) and satisfaction with SMASH (4.5/5 Likert Scale).²⁶ The SMASH group

showed clinically meaningful reductions in resting SBP compared to the SC group (see Fig 6). At both 3 and 6-mo time points, 57-86% of SMASHers were below JNC8 BP control cutoffs compared to <25% for the SC group. We examined ED rates during the 6-mo periods prior to vs during and following the trial (6-mo period) the trial. The SMASH group showed an 87.5% reduction compared to a 20% reduction in the SC group.²⁶

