D.1. Design and Randomization: Subjects will be drawn from Fetter Health Care Network (FHCN). It is the sole FQHC center in the 4-county area (8 clinics) and provides ~60% of routine AA healthcare in the 4 county area.¹⁰⁷ A support letter from the FQHC network is included. EMR files indicated they have ~2,619 AAs (21-59 yrs old; mean age=45.3yrs) with sole diagnosis of uncontrolled HTN. We will use the 8 practice sites in a 2 arm RCT design (n=192) with clinic as unit of randomization and patient as unit of analysis. All primary healthcare providers across the 8 clinics have agreed to participate if selected. Each clinic has a minimum of 2 primary providers (at least 1 MD and 1 or more NPs and/or PAs per clinic). Thus, 2 providers per site will be recruited. Each will have 12 of their patients recruited (24 per clinic). Given our ~90% participation rate in previous FQHC studies^{25,108,109} and 93% SMASH participation rate, we anticipate no recruitment problems. The Medical University of South Carolina Family Medicine and Internal Medicine clinic population will be an additional recruitment resource if needed.

D.2. Participants: With consideration of the relevant biological variable of gender, we will recruit 192 AA 21-59 yr old uncontrolled HTNs with equal numbers of males and females that meet the following inclusion/ exclusion criteria: 1) SBP ≥ 140 mmHg on most recent clinic visit over last 12 mos and at BP screening and recruitment visits; 2) MPR < 0.85 over last 3 mos; 3) 24-hour SBP ≥ 130 mmHg (HTN cutoff) to help rule out white coat HTN.^{76,110} SBP used as selection variable since most AA HTNs < 60 have systolic or combination systolic/ diastolic HTN and for most patients, controlling SBP also results in DBP control;^{27,111,112} 4) no other known chronic diseases (e.g., diabetes, chronic kidney disease (GFR < 50 ml/1.73 m²/min), cancer, renal dialysis, heart attack, coronary artery bypass, arterial stent, substance abuse (e.g., > 21 drinks/week), psychiatric illness, Beck Depression Inventory¹¹³⁻¹¹⁵ > 13 , able to speak, hear and understand English; take own BP and meds; 6) owns smart phone with current data plan; 7) primary care MD's assent patient able to participate and 8) no planned pregnancy or vulnerable population (e.g., pregnant or nursing women, prisoners).

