SDT constructs	TSRQ Autonomous Self-Motivation (α .81-.84)(Appx.8) ^{97,122} Perceived Competence Scale (MASES-R) (.92, test-retest [3 mos.] .51) (Appx.7). ^{101,123,124}	Baseline,3,6,12,18 mos
Exploratory Outcomes		
Cost effectiveness	Costs of additional personnel time, SMASH devices, ED visits, unplanned outpatient visits & hospitalizations, workdays lost.	First 6 mos of trial & through post-trial follow-ups
Physical Risk Factors	TC, LDL, HgA1c, blood glucose from FQHC standard care via MedCorp (intra-assay variations all <5%; inter-assay variations 3.3% to 6.6%)	Baseline,6,12,18 mos
Potential MA Mediators	HTN Knowledge (.70) (Appx.9); ^{129,130} Short Test of Functional Health Literacy (S-TOFHLA)(.68) (Appx.10); ¹³¹⁻¹³³ SF-8(α .87) (Appx.12); ¹³⁵ Med Side effects (Appx.11); ¹³⁴ Adverse events; Pittsburgh Sleep Quality Index (sleep quality) (.83; test-retest [1mo, 12 mo] .85, .68) (Appx.16); ^{138,139} Beck Depression Inventory (BDI) (0.82-0.92); (Appx.13); ¹¹³⁻¹¹⁵ Perceived Stress Scale (PSS) (.84-.86; test-retest [2 day] .85)(Appx.15); ^{136,137} Illness Perception Questionnaire (IPQ-R; perceived disease severity); .84, test-retest [3 weeks,6 mos] .74.,.74) (Appx.17); ¹⁴⁰ Questionnaire on Quality of Patient & Physician Interaction (QQPPI)(Appx.18). ¹⁴¹	Baseline,3,6,12,18 mos
Values/Beliefs/Goals	Values, Beliefs, Goals (test-retest [1 mo].85) (Appx.14). ¹⁰⁶	Baseline,3,6,12,18 mos
Anthropometrics	Ht./Wt./Girth (Appx.6).	
Sociodemographics	Age, education level, income, type of healthcare insurance	Baseline
Feasibility	Recruitment and Retention rates.	End of trial
System Usability	System Usability Scale (Appx. 19); ^{146,147} Patient/Provider SMASH/SC Treatment Satisfaction & Usability Scale (TSUQ) (α .82-.96, test-retest [1wk] .98) (Appx.20); ^{144,145} User Version of Mobile App Rating Scale (uMARS) (.90, test-retest [2, 3 mos] .66, .70) (Appx.21). ^{142,143}	At 6 mos (All subjects) After all subjects complete 6 mos trial (Providers)
Process/uptake	Patient level (e.g., connection/reloads of MedMinder, BP uploads via phone & opening of messages /education info) & provider level (e.g., opening of patient summary reports & phone alerts).	First 6 mos of trial

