D.10. Quantitative Analyses: AIM1 Primary outcome measures are % of subjects with >0.90 MA from MedMinder and % within JNC8 clinic resting BP guidelines (<140/90 mmHg). Secondary analyses will assess resting & ambulatory BP levels (e.g., 24-hr, daytime/nighttime BP level changes) & MA indices (i.e., MPR score changes). Intent-to-Treat (ITT) sample analyses will be used along with multiple imputation methods for missing end-of-study outcomes.^{149,150} To assess relationships between intervention outcomes and intervention status (SMASH or SC) at end of the active trial period (6-mo visit, primary endpoint), two-sided Cochran-Mantel-Haentzel chi-square tests for unadjusted differences in proportions will be used. Adjusted differences in proportions at the 6-mo visit will be compared using logistic regression. To assess relationships over time, we will use a generalized linear mixed models (GLMM; generalized estimation equation [GEE]-type models) analytic model with group (SMASH vs SC) & time (3, 6, 12 & 18 months) included as fixed effects and FQHC practice site as a random effect to account for clustering within FQHC practice site/MD.¹⁵¹⁻¹⁵³ In the first set of models, baseline measurement of the dependent variables (e.g., MA or BP levels) will be included as adjustment variable. The test of primary interest is F-test for the treatment x time interaction, which will reflect a difference in change between the 2 groups over the study. If a statistically significant treatment x time

interaction is found, we will obtain odds ratios for SMASH vs SC groups at each of the study time points.

A mixed effects model (MEM) will be used to compare the primary continuous outcome measures (e.g., tray or MPR derived MA scores or BP levels) for the two groups over the study period. Modeling will be carried out as described above. We will estimate resting and 24-hr BP changes and MA (MPR) changes for each subject over the trial (baseline, 3, 6, 12 & 18 months) and the within subject longitudinal trajectories (e.g., slopes) and summarize as the mean longitudinal trajectory within each group. ICCs and variance estimates will be obtained of efficacy outcomes and covariance structure of the longitudinal scores for determination of sample size (and hence adequate power) for a future effectiveness RCT.

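### The exploratory cost analysis (Aim 3b) neither collects nor adjusts for health-care use before enrolment; adding it is a cheap guard against chance imbalance with 4 v 4 clinics and would gain precision.

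*Combined protocol and SAP*

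**What the plan says.** Section D.10, Aim 3, defines the economic benefit as a contrast between arms: "We will define benefits as difference in cost of health services use and lost worked days between SMASH and SC groups". The use that is costed is "costs of emergency department (ED), outpatient and hospital visits during the 6-month trial and most importantly, the 12 months following trial completion". The cost-effectiveness row of Table 3 gives the same window: "First 6 mos of trial & through post-trial follow-ups". Blood pressure, ambulatory pressure, the self-determination scales and the laboratory risk factors all have a baseline time point in that table; the cost row has none.

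The cost model is a GLM for "patient level healthcare costs and patient lost income adjusting for patient demographics and comorbidities". Utilisation and lost workdays are handled in the same way with a count model. Prior use or prior cost is not listed for either. Adjustment for the baseline value of the outcome is stated for the Aim 1 models: "In the first set of models, baseline measurement of the dependent variables (e.g., MA or BP levels) will be included as adjustment variable". Aim 2 and the laboratory outcomes refer back to that modelling; the cost paragraph sets out its own models and does not.

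Section D.1 makes "clinic as unit of randomization and patient as unit of analysis", with 8 clinics and 24 patients in each; D.8 gives 4 clinics per group.

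Section C.1.4 shows that two pilots did look back. Trial #2 compared emergency visits in the 6 months before with the 6 months during the trial and reported a "57.5% reduction (7 vs 3 ED visits) whereas the SC group showed a 5.7% reduction (13 vs 12 ED visits". It valued the savings at $23,692 (SMASH) and $5,923 (SC). Trial #3 also compared emergency use with the preceding 6 months.

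**The concern.** Past use of emergency and hospital care can reasonably be expected to predict later use. If the arms differ in it at entry and the analysis starts the clock at enrolment, the part of the difference that persists is counted in the benefit estimate. The planned covariates offer little protection. Sections D.2 and Protection of Human Subjects exclude patients with another known chronic disease, so comorbidity varies little at entry, and comorbidities that develop later arise after randomisation. The sensitivity analyses adjust for blood pressure control, which is also a post-randomisation outcome.

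What is at stake is the accuracy and precision of the exploratory savings estimate. Section A.5 looks ahead to reimbursement by public and private payers, and a savings figure that cannot be separated from prior use would be weak support for that.

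**Working it through.** **1. Reproduce the pilot figures (C.1.4, Trial #2).** Emergency visits before and during the trial were 7 and 3 for SMASH, and 13 and 12 for SC.
- Cost per visit: $23,692 / (7 − 3) = $5,923 for SMASH; $5,923 / (13 − 12) = $5,923 for SC. Both savings reproduce.
- The printed percentages do not quite match the counts: (7 − 3)/7 = 57.1% (printed 57.5%) and (13 − 12)/13 = 7.7% (printed 5.7%). The counts are used below.

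**2. Apply the two methods to the pilot counts.**
- During-trial difference only, as now planned: 12 − 3 = 9 visits; 9 × $5,923 = $53,307.
- Difference in change, as in the pilot: (7 − 3) − (13 − 12) = 3 visits; $23,692 − $5,923 = $17,769.
- Ratio: 9 / 3 = 3.0. The gap before the trial was 13 − 7 = 6 visits.

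**3. Allow for partial persistence.** With prior use as a covariate of slope b, the adjusted benefit is 9 − 6b visits.

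| b | Adjusted benefit (visits) | 9 / adjusted |
|---|---|---|
| 0 | 9.0 | 1.0 |
| 0.25 | 7.5 | 1.2 |
| 0.5 | 6.0 | 1.5 |
| 0.75 | 4.5 | 2.0 |
| 1 | 3.0 | 3.0 |

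**4. Allow for unknown arm sizes.** D.8 suggests a total of 22 for this pilot, but the documents give no split. Per patient and with b = 1, the ratio is 3.0 at 11:11 (SMASH:SC), 2.2 at 10:12 and 4.1 at 12:10. It runs from 1.1 at 8:14 to 8.0 at 14:8.

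**5. Test the pilot's prior gap.** With equal arms and independent visits, 13 or more of 20 visits in one arm has an exact two-sided p of 0.26. Treating the four counts as independent Poisson, the change-based difference of 3 has a standard error of √(7 + 3 + 13 + 12) = √35 = 5.9.

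**6. Size the chance imbalance in the planned trial.** With 4 clinics per arm and m = 24 patients per clinic, the between-arm difference in mean prior use, in patient-level SD units, has standard deviation √(2 × (1 + (m − 1) × ICC) / (4m)).
- ICC 0: √(2 × 1 / 96) = 0.14.
- ICC 0.04: √(2 × 1.92 / 96) = 0.20.
- ICC 0.10: √(2 × 3.30 / 96) = 0.26.

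The 0.04 is the value D.8 states for tray-based adherence and systolic pressure. Applying it to health-care use is an assumption, hence the range. The documents give no SD for use or cost, so these figures cannot be turned into dollars.

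**The case against.** The strongest reply is that clinics are randomised, so comparing the arms after enrolment is unbiased over the randomisation. That stands. A reader might infer that existing clinic differences will be booked as SMASH savings. The documents do not support a direction: an imbalance is as likely to hide a saving as to create one.

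A reader might also infer from the pilot that the benefit will be tripled. The documents do not support that either. The threefold figure needs equal arms and full persistence. The 7 v 13 gap is compatible with chance, and the change of 3 visits is too imprecise to serve as a stable denominator. Nothing shows that the gap came from clinics: Trial #1 assigned individual participants, and Trial #2 is described as following the same protocol apart from message delivery. The planned trial has 192 patients, against about 22 in that pilot.

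A third inference is that the cost-effectiveness ratio could be wrong in size or sign. D.10 describes the ratios as setting the cost of SMASH against clinical change, and defines savings in use separately as benefit. Read that way, prior use affects the benefit and leaves the ratios alone, unless their cost is taken net of savings.

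Two mitigations deserve credit, but neither closes the gap. Demographic adjustment may absorb some of an imbalance. The Introduction to Revised Application promises clinic as a random effect; this is not restated for the cost models, and it would widen the interval without removing a difference between arms. The same section notes that "Lead site has 7.3 providers & generates ~45% of patient encounters", while the other seven clinics are similar in size. That shows heterogeneity in size; it does not show different emergency use. Finally, the outcome is exploratory, and no primary or secondary inference depends on it.

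**Conclusion.** The point holds as a cheap improvement to an exploratory analysis. The plan has no pre-enrolment measure of health-care use or lost workdays and no adjustment for it, although the sponsor used such a window for emergency visits in two pilots. The consequence is exposure of the benefit estimate to chance imbalance in either direction, together with lost precision. It is not systematic bias.

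For the planned trial, the best available size is a standard deviation of about 0.20 patient-level SD for the between-arm gap in mean prior use (0.14 to 0.26 over ICC 0 to 0.10). This assumes equal clinics of 24, and only the persistent share of the gap reaches the benefit estimate. The pilot's 9 visits against 3 illustrates the mechanism and does not forecast the error. The gain in precision cannot be sized, because the documents give no correlation between prior and later use.

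**What to change.** In Table 3 (cost-effectiveness row) and D.10 Aim 3, add a 6-month pre-enrolment window, the length used in the pilots, for emergency, hospital and outpatient use and for lost workdays. Collect it in both arms from the same source as the follow-up data, and name that source. Enter each patient's pre-enrolment value as a covariate in the cost, utilisation and workday models. State in the same place how clinic clustering is handled in those models, and whether the cost in the cost-effectiveness ratios is net of savings in use.

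The cost is one look-back extraction or one baseline item per patient, plus a few lines of text. Screening already consults records for the last clinic visit and the 3-month possession ratio. The drawback is imprecise recall for workdays, and for any use that is self-reported, since the documents name no record source for emergency or hospital visits. The workday question has to be in place at enrolment, because it cannot be recovered reliably later.
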